Background: In a variety of visual search experiments, both basic and clinical, the data have been consistent with a situation where the variability of the signal (or target) is greater than the variability of the noise (distractors). As an example, in screening for breast cancer, this would mean that the variability of backgrounds in mammograms would be less than the variability in actual signs of cancer (the signal in these “signal detection theory” (SDT) terms. The classic sign of this greater signal variability is a “zROC” function with a slope < 1 – typically around 0.6. A slope of 1.0 is indicative of an equal variance 2AFC task; that is, the same amount of variability in the signal and the noise. The present experiment is part of a series where we systematically vary the parameters of a simple 2-alternative forced-choice (2AFC) task where participants decide if a stimulus is “good” or “bad”. Participants can also be helped by a simulated AI system. This is our **Human-AI Collaboration Tester (HAICT)**.

For the HAICT task that we have been testing in this series of experiments, we would expect equal variance, but we think it would be worth checking so we will systematically vary prevalence which will shift criterion. That will sweep out an ROC curve that we can examine.

We will also test the Second Reader faux-AI in order to determine if low prevalence makes Second Reader worse.

- (H1): We expect to replicate the finding that human criteria become more conservative as prevalence declines.
- (H2): We predict that the slope of the resulting zROC will be 1.0.
- (H3): We hypothesize that low prevalence will make Second Reader AI less effective because the positive predictive value of its comments will be low.

1. **Dependent variable.** Describe the key dependent variable(s) specifying how they will be measured.

The main dependent variables of interest are accuracy (and the signal detection derivatives of accuracy, d' and c), reaction time, and subjective ratings on the survey following each block.

2. **Conditions.** How many and which conditions will participants be assigned to?

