This series of experiments investigates how changing the input from a simulated AI can affect the decisions made by human observers in a two-alternative forced choice task (like the decision to recall a woman for further examination in mammography). We have developed a paradigm called the Human-AI Collaboration Tester (HAICT) that allows for efficient testing of interactions between a human and a simulated AI.

The observers' task in all conditions is to give a 2AFC decision about whether a stimulus is "bad" or "not bad." To use language roughly mimicking a medical diagnosis, each stimulus is referred to as a "case." Observers are asked to make a 2AFC decision about arrays of colored shapes. The decision is made based on the predominant color of the case. The number of elements of each color are drawn from one of two normal distributions, one for positive (bad) stimuli and the other for negative (not bad) stimuli.

The results from previous HAICT experiments (3 and 4) showed that human performance in the Second Reader condition drops off significantly at low prevalence. Performance in the Second Reader condition was better than Baseline when the prevalence of bad cases was 50% but was significantly worse than Baseline when prevalence was only 10%. In this experiment, we manipulate the prevalence of "bad" cases in the Second Reader and Baseline conditions. Four different prevalence rates will be tested – 10%, 33%, 67%, and 90%. Observers will complete 8 blocks (2 AI rules x 4 prevalence rates), and block order is random.

AI rules to be tested:

1. Baseline - No AI input. Observer classifies each case as "bad" or "not" bad on their own.
2. Second Reader - The observer makes an initial decision about every case. The AI silently classifies stimuli using a conservative criterion ($c = 0.5$). The logic for the conservative criterion is that the second reader is being used to cut down on false positive responses and so it is intended to question positive human responses that

might be marginal. If the observer and AI disagree, then the AI informs the human observer. The observer is then given a chance to either change their response or go with their first opinion.

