As in Experiments 1-5, the AI d-prime is fixed at 2.2. Feedback is known to increase the prevalence effect, so feedback will be given in both the practice and the test trials. Observers will complete 20 practice trials and 200 test trials in each block. Immediately after each block is completed, observers will be shown a summary of their performance. After the Second Reader blocks, they will also be asked to answer three subjective questions about the usefulness of the AI (see "Files" for more details).

3. Analyses. Specify exactly which analyses you will conduct to examine the main question/hypothesis.

First, we summarize the number of hits, true negatives, misses, and false alarms in each block. From this, we can calculate the accuracy, the positive predictive value, sensitivity (d-prime), and the criterion for each observer under each of the different conditions. Given measures of performance at 4 levels of prevalence, we can estimate the ROC curve ($pHit \times pFA$) and the zROC function ($zHit \times zFA$). We will test the hypothesis that the slope of the zROC is equal to 1 (the consequence of an equal variance 2AFC task).

4. More analyses. Any secondary analyses?

We will look to see if the observers' subjective opinions about the AI are correlated with variables such as the empirical d-prime, or the positive predictive value.

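### H2's predicted zROC slope of 1 is the null of its only test, so non-rejection would not support equal variance; report the slope with an interval, on Baseline responses.

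*Protocol*

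**What the plan says.** The Protocol's Background states H2 as "We predict that the slope of the resulting zROC will be 1.0". It introduces the question as a check: "we would expect equal variance, but we think it would be worth checking". The contrast it offers is the slope below 1 seen in other visual search work, "typically around 0.6".

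Under 3. Analyses, the only step for H2 is "We will test the hypothesis that the slope of the zROC is equal to 1 (the consequence of an equal variance 2AFC task". The slope comes from zHit against zFA at four prevalence levels. No alpha, interval, margin, decision rule or fitting method is given. The same section computes accuracy, positive predictive value, d' and criterion "for each observer under each of the different conditions", but does not say which responses, or which level of pooling, feed the slope.

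Under 2. Conditions, a Second Reader trial on which human and AI disagree has two answers: "The observer is then given a chance to either change their response or go with their first opinion".

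The Data analysis section of the combined protocol and SAP reports 12 analysed observers and defines zHit, zFA, d' and c. It does not mention a zROC slope.

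**The concern.** A test whose null is the predicted value can refute the prediction but cannot establish it. If the result is non-significant, the reader needs to know which slopes the data rule out, and the plan offers nothing for that. At stake is whether a report of H2 could claim equal variance when moderate departures remain compatible with the data.

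Two unstated choices add to this. Final Second Reader answers mix the observer with an AI of fixed d' and criterion, so they do not test the observer's own variances. Some ways of fitting a line through four noisy points are also biased when the points lie close together.

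**Working it through.** The plan gives no power, precision or slope standard error, so there is no figure to reproduce. The results below are illustrative.

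**Inputs from the documents.** 12 analysed observers; 200 test trials per block; prevalence 10/33/67/90%, hence 20/66/134/180 positives; AI criterion c = 0.5; "As in Experiments 1-5, the AI d-prime is fixed at 2.2".

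**Assumed, because the documents do not give them.** Human d' mean 2.0 (SD 0.3), block-to-block criterion SD 0.15, two-sided alpha 0.05, and a criterion shift of 30, 50 or 100% of the ideal, where ideal c = ln((1-p)/p)/d'. At d' 2.0 and 50% shift, c = 0.5 x ln(9)/2 = 0.549 at 10% prevalence and 0.5 x ln(67/33)/2 = 0.177 at 33%, with the signs reversed at 90% and 67%.

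**1. What non-rejection shows.** Simulation with 1000 studies per cell, Baseline only, maximum likelihood on counts, jackknife over observers, t on 11 df. Entries are percentages of studies at 30/50/100% shift.

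| True slope | Slope 1 not rejected | 95% CI includes 1 and excludes 0.6 |
|---|---|---|
| 1.0 | 94/94/95 | 73/92/95 |
| 0.9 | 92/86/66 | 51/77/66 |
| 0.8 | 80/61/15 | 26/41/15 |
| 0.6 | 51/14/0 | not computed |

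At a true slope of 0.8, orthogonal regression gave non-rejection of 77/59/18%, and a second orthogonal run gave 68/49/13%. Per-observer fits under different assumptions (d' 1.8 or 2.2, other criterion shifts) gave 34-86%. The last column shows that excluding 0.6 does not rule out 0.8 or 0.9.

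**2. Which responses.** Suppose a constant share w of disagreements is switched to the AI's answer. Then, whatever the human-AI correlation:

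- final hit rate = (1-w)H + w x 0.726, where 0.726 = Phi(1.1-0.5)
- final false-alarm rate = (1-w)F + w x 0.055, where 0.055 = Phi(-1.1-0.5)

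Example: an equal-variance observer with d' 2.0, 50% shift and w = 30%.

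- Initial hits 0.674/0.795/0.880/0.939 and false alarms 0.061/0.120/0.205/0.326: slope 1.
- Final hits 0.689/0.774/0.834/0.875 and false alarms 0.059/0.100/0.160/0.245.
- End points: zHit runs from 0.49 to 1.15 and zFA from -1.56 to -0.69, so the slope is about 0.66/0.87 = 0.76. The orthogonal fit to all four points gives 0.755.

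The size depends on how observers switch (no sampling error, human d' 2.0):

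- Constant share: 0.91/0.90/0.88 at w = 10%, 0.76/0.75/0.75 at 30%, 0.63/0.63/0.65 at 50%.
- Only judgements near the criterion switched, AI independent: about 0.97 (within 0.3 SD), 0.93-0.94 (0.5 SD) and 0.88-0.90 (0.75 SD). Smoothly declining switching goes as low as 0.86.
- Only negative answers switched: 0.98-1.02, almost no bias.

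With AI d' 2.5, the maximum in the combined document's HAICT methodology, the constant-share slopes barely change: 0.92-0.89, 0.78-0.76 and 0.64-0.65.

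**3. Which fit.** Baseline only, true slope 1, at 30/50/100% shift. Least squares of zHit on zFA within each observer has mean slope 0.79/0.94/1.00 and false rejection 26/14/6%. zFA is measured with error (only 20 negatives at 90% prevalence), which flattens the line. Maximum likelihood falsely rejects in 6/6/5% and orthogonal regression in 5/6/6%. Least squares on counts pooled over observers has mean slope 0.99-1.00.

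**The case against.** **It is only a check.** The Background says so, a test of a predicted point value can refute H2, and no decision rule is written. A reader might infer that the sponsor means to treat p > 0.05 as proof of equal variance. Neither document says that. Calling it a check still does not make non-rejection evidence for slope 1. A 95% interval and the matching test agree on rejection, but only the interval shows what else fits the data.

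**H2 concerns the observer's own decisions.** The Background ties the zROC to the HAICT task itself and brings in Second Reader in a separate paragraph, for H3. Baseline is therefore the natural reading. A reader might infer that final Second Reader answers will enter the slope, but no passage says so, and the per-condition wording describes other measures. This largely stands: what remains is a choice to be written down.

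**The bias figures depend on the model.** This also stands. Slopes near 0.6 need a high, constant switching rate. The AI is meant to question marginal positive answers, and switching confined to marginal judgements gives a much smaller effect. Least-squares bias arises only with per-observer fits and a small shift. No passage names least squares, and feedback is given because it strengthens the prevalence effect, which favours a larger shift.

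**Conclusion.** The concern holds in limited form. As written, the test can count against H2 but cannot support it. Under the stated assumptions a true slope of 0.8 escapes rejection in roughly 15-80% of studies. It would be wrong to call the test uninformative: at a 50% or larger shift, a true slope of 0.6 is rejected in 86-100% of studies (100-14 and 100-0), though in only 49% at a 30% shift.

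The response set and the fit are unstated details, not demonstrated errors. Each could pull the slope below 1 in an equal-variance observer, by an amount that rests on unknown switching behaviour and criterion shift. Importance is minor to moderate.

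**What to change.** - Report H2 as the zROC slope with a 95% confidence interval over observers, for example by jackknife. State which slopes it excludes, including whether it excludes 0.6, and note that excluding 0.6 leaves 0.8-0.9 open. Do not read p > 0.05 against 1 as confirming H2.
- Name Baseline responses as the main set and initial Second Reader responses as a sensitivity analysis. Do not use final Second Reader responses for this test; they remain available for H3.
- If the slope is fitted per observer, use a method that allows error in both zHit and zFA.
- The combined document reports testing as done, so label choices made after the data were seen as post hoc.

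The cost is analysis wording, one fit and one interval. The downside is that H2 may be inconclusive. At true slope 1 with Baseline only, the median interval is 0.69-1.44, 0.79-1.26 or 0.87-1.15 at 30, 50 or 100% shift, and it contains both 1 and 0.6 in 21, 2 or 0% of studies. Adding initial Second Reader responses narrows it to 0.77-1.29, 0.85-1.18 or 0.91-1.10, if those responses behave like Baseline.

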## Introduction

Artificially intelligent (AI) systems are increasingly common and competent collaborators for humans performing a variety of everyday tasks. There are AI systems designed to help us park our cars, translate our voices into text messages, and filter out our spam email. AI collaborators have also been integrated into the workflows of expert humans performing socially important, and even potentially dangerous, jobs — e.g., assisting air traffic controllers in preventing midair collisions. Interestingly, some AI systems are designed to act as second observers to assist humans in making important *perceptual decisions*: Airport baggage screeners use AI support to decide whether there is a weapon in a bag; radiologists use AI support to decide whether a suspicious region on an X-ray is cancer; and law enforcement use AI support to identify suspects in surveillance video. What makes these examples different from AI sorting our email, or calculating flight paths, is that they all involve a human and a machine making a decision about the same perceptual stimulus (e.g., “Is that object in this suitcase a weapon or a dumbbell?”).

If humans and AI are working together, even the most talented AI is only useful if its human collaborator can and will take advantage of its information. If the human does not trust the AI, she may ignore its advice (Beck et al., 2007). There are many different possible rules for combining the same human and AI information (e.g. Does the AI offer its information before, during, or after the human’s initial decision?). These rules can produce different outcomes. We frame this situation in terms of signal detection theory (Hautus et al., 2021; Macmillan & Creelman, 2005). In that context, changing interaction rules can shift  $d'$ , criterion, or both. Moreover, the rules interact

---

 Note: In the psychophysical literature,  $d'$  is often called “sensitivity”. However, in the medical literature, “sensitivity” refers to the true positive (TP) or hit rate. Accordingly, we will try to avoid using the term, “sensitivity” at all.

strongly with task variables (e.g. How prevalent are positive cases?). The interaction of task and rule can change the human user's attitude / trust in the AI (Hoff & Bashir, 2015). This, in turn, influences the combined results for human plus AI.

[figure not shown]
AI support for perceptual decision making is wide-spread. We will focus our discussion on medical images (Greenes, 2014) recognizing that the issues are similar in other domains from conversing with your car (Strayer et al., 2016) to automating airport screening [Hättenschwiler, 2017 #13395]. In medical image interpretation, much of this work falls under the heading of Computer-Aided Detection (CADe) and Computer-Aided Diagnosis (CADx) (Li & Nishikawa, 2015).

If experts were perfect at detecting and identifying clinically relevant findings in images, there would be no interest in CAD, but experts evaluating medical images make more mistakes than we would like, and CAD helps less than we would hope. Precise error rates in actual clinical practice are hard to establish though 20-30% appears to be a reasonable estimate in many radiologic domains (reviewed in Berlin, 2007). Some of these errors are, in a sense, desirable. For instance, a suspicious spot on a mammogram should be referred for further testing, even if it subsequently turns out to be a false positive. Of course, if AI could reduce these 'desirable' false positive errors, that would save unnecessary testing, expense, and worry. False negative / miss errors can have a higher cost in cases where early detection improves outcomes (Monticciolo et al., 2017).

---

Kundel and colleagues (1978) provided a useful 3-part taxonomy for false negative (“miss”) errors, dividing them into search, recognition, and decision errors, based on eye movements recordings. Search errors are those where the eyes never fixate on the target at all. In recognition errors, the eyes briefly (<500 msec) fixate the target but then move on, as if the observer failed to recognize that something interesting had been fixated. Decision errors are those where the observer (and the observer’s eyes) scrutinize the relevant stimulus location but fail to identify the target.

**Figure 1: Two-alternative forced-choice decisions as signal detection problems.**

In their simplest form, decision errors can arise when the observer is faced with a two-alternative forced-choice decision (e.g. Is this cancer or not?). In the terms of signal detection theory, as cartooned in Figure 1, truly negative and positive cases can be thought to produce overlapping distributions of internal response values within the observer. To make a decision, the observer must establish some ‘criterion’, ‘c’; declaring all values above criterion to be positive and those below to be negative. The separation between the positive and negative distributions determines the difficulty of the decision and can be quantified by the parameter,  $D'$  (though the situation is

more complex and other metrics are more useful if, for example, the variance of the two distributions is not the same). When the distributions overlap, the observer *must* make errors: False positive (FP) or False alarm errors, shaded red, and False Negative (FN) or miss errors, shaded green. Shifting criterion can change the mix of errors but cannot eliminate them. A manipulation that increases  $D'$  reduces errors.

Two observers will typically perform better than either alone, especially if the ‘noise’ that degrades their performance is not identical. The relationship of two observers in SDT terms has been formalized by Sebastian and Geisler (2018). A CAD AI that offers its own assessment of the stimulus can be thought of as a second observer. The focus of our interest is in the interaction of that second observer with a human who is making the ultimate decision.

Search and recognition errors can arise when the perceptual task involves spatial uncertainty. If the task involves a search for possible targets (e.g. signs of breast cancer), it is possible to fail because you never looked at the target (search errors) or because, when you looked at the target, its importance was not registered (recognition errors). The use of AI to reduce these errors is important but not considered in this experiment.

As we are framing the Human-AI interaction in perceptual decision making, there is an error-prone human observer and an AI that might be useful. The resulting human-AI interaction can be formalized as a signal detection problem with two observers (Bartlett & McCarley, 2017; Bechar et al., 2009). For example, take a human and an AI, each with  $d'$  of 2.5 (comparable to performance in screening mammography). If the two observers are uncorrelated, the optimal joint  $d'$  would be about 3.5. As Bartlett and McCarley (2017) note, however, “In practice, unfortunately, people

often interact with automated aids in a suboptimal way". They may overweight or underweight the AI advice. The core problem is that there is no one optimal solution that covers all Human-AI interactions. To offer a trivial illustration, if the human is simply guessing and the AI is perfect, the obvious rule is to use the AI. If the situation is reversed, the obvious rule is to ignore the AI. The optimal use of the AI, therefore, depends on the details of the specific Human-AI interaction. Unfortunately, it is not practical to test a range of modes of interaction in real-world clinical situations. Expert observers are a limited resource and interventions (e.g. don't use AI on the next N patients) are often unethical or impractical in the real world. Our goal is to develop a "Human-AI Collaboration Test (HAICT) that can be used in the lab to identify candidate interventions that could be practically tried in real-world settings.

We can identify a non-exhaustive set of factors that will influence the AI-human interaction.

- 1) Absolute and relative skill of the human and AI: This defines a 2D space of conditions where the human and AI might both be very skilled or not or where one is more skilled than the other.
- 2) Signal & noise variability: The physical signal, presented to the human and/or the AI has some intrinsic variability. That variability could be different for signals (Do all masses look alike and are they all imaged with equal fidelity?) and for 'noise' (Do other possible masses all look alike or do they come in a wide range of forms?).
- 3) Correlation of AI and human responses; Are the human and AI responding in the same way to the same thing? The potential benefit of an AI declines as its correlation with the human increases. Thus, the situation is different if both parties are limited by the same physical signal/noise ratio as opposed to a condition where the human is looking at an X-ray while

the AI is basing its response on some entirely different measurement. Sebastian and Geisler (2018) have provided an SDT-based method for estimating the correlation between two observers.

- 4) Feedback: In many real-world settings, it is not available or available only incompletely, in aggregate, and/or after a significant delay. Consider screening mammography where some AI true positives will provide an immediate form of feedback when the radiologist clearly sees that CAD has marked something they found or missed. Feedback about other CAD responses would have to wait for subsequent follow-up (e.g. Was it a hit or a false alarm?).

In the case of miss errors, by either the human or the AI, it is possible there is no feedback.

- 5) Costs and benefits of different outcomes: In mammography, for example, FP errors carry modest risk and some real psychological and financial costs. The costs of FN errors are much greater. A similar situation applies to airport security screening. The could also be operational costs if, for example, adding AI doubled the time or the cost of an exam.
- 6) Target Prevalence: Particularly in screening situations, target prevalence is an important variable. Breast cancer is rare in a screening population. Real threats are even rarer at the airport checkpoint. This obviously interacts with costs and benefits. Are 100 or 1000 FP errors more or less expensive than one FN error? Prevalence is known to influence human behavior (Levari et al., 2018; Wolfe et al., 2005).

This partial list describes a vast dataspace. It would be neither practical or fruitful to systematically cover it with experiments. One possible solution would be to model the effects. A valiant effort was made by Bechar et al (2009) who proposed to compute “An Objective Function to Evaluate Performance of Human-Robot Collaboration in Target Recognition Tasks” (Bechar et al., 2009).

Bechar et al created a linear model that incorporates many (but not all) of the variables described above and they could draw some interesting conclusions from the output. For instance, for their conditions, the utility of the AI increases as target prevalence increases; a potentially depressing conclusion for CAD systems deployed to help with the detection of rare targets. Their conclusions include the statement, “Since the number of parameters is large and, in addition, there are interactions between the parameters, it is difficult to predict the system performance”.

[figure not shown]
How, then, can progress be made on deciding on the best use of an AI system? In this project, we propose a testbed that captures critical aspects of human-AI interaction in a signal detection paradigm. The idea is that a simple, 2-alternative forced-choice (2AFC) task can be tailored to have the properties of the real-world situation. Stimuli can be created to constrain the  $d'$  of the observer and the AI. The prevalence of targets can be set along with a reward structure for different types of correct and incorrect responses. Feedback can approximate the real-world situation. Having built a task with critical similarities to the real-world task, it is possible to test non-expert observers in relatively short experiment that manipulate factors like the timing of presentation of AI information or the criterion used by the AI. Such experiments will not eliminate the need to test hypotheses with real experts doing the real task. However, results from this Human-AI Collaboration Test (HAICT) can guide clinical testing to the more promising possibilities.

In the experiment described here, we take a single, hypothetical AI and use it as a *second reader* – presenting the AI opinion after the human has offered an initial reading.

